**Subjects randomized prior to IDMC approval to convert Day 71 Visit to telephone call:**

- If a subject reaches the Day 71 Visit prior to the IDMC approval to convert the Day 71 Visit to a telephone call, the Day 71 Visit must be completed to assess safety parameters, including AEs, vital signs, pulse oximetry, ECG, physical exam, clinical laboratory values, and spirometry. No telephone call is required on this day if a visit is conducted.
- If the IDMC does not approve to convert the Day 71 Visit to a Telephone Call, subjects will proceed as per the bullet above.

**Subjects randomized after IDMC approval to convert Day 71 Visit to telephone call:**

- The Day 71 Visit will be changed to a Day 71 Telephone Call to assess AEs. No visit is required on this day if a telephone call is conducted.

### 8.1.3.2 Part B

Part B comprises Treatment Period 3 and is optional.

#### 8.1.3.2.1 Treatment Period 3

In order to continue into Treatment Period 3 the subject must sign the Part B informed consent form (ICF) or assent, as applicable. The ICF should be signed before the Day 85 Visit to allow for delivery of study drug for Treatment Period 3.

Study visits will occur on Day 85 (also the last visit of Treatment Period 2) and Day 113 to allow for a full 28 days of study drug (inhaled study drug and oral ivacaftor).

On Day 86 and Day 87, until the telephone call is no longer required by the IDMC, subjects will have a telephone call for safety purposes (e.g., inquire about AEs). If necessary, the subject may be asked to return to clinic to follow up on a new medical problem.

The first dose of both ivacaftor and inhaled study drug in Treatment Period 3 will be administered at the Day 85 Visit, after completion of the Day 85 pre-dose assessments.

If the first dose of study drug (inhaled study drug and oral ivacaftor) administered in the clinic on Day 85 is taken in the morning, the second dose will be taken that evening. The last home dose of the twice daily study regimen in Treatment Period 3 will be taken on the evening of Day 112 and no dose will be taken on Day 113.

If the first dose of study drug (inhaled study drug and oral ivacaftor) administered in the clinic on Day 85 is taken in the afternoon, a second dose will not be taken that evening. The last home dose of the twice daily study regimen in Treatment Period 3 will be taken on the morning of Day 113, at least 4 hours before the Day 113 Visit.

Subjects should only take study drug at a maximum of twice daily.

Subjects will remain in the clinic for a total of 2 to 4 hours after dosing with study drug at the Day 85 Visit until the IDMC provides approval to only require subjects to remain in clinic for 1 hour post-dosing. The duration (2 to 4 hours) each subject stays in clinic for observation will be left to the discretion of the investigator. If the IDMC does not approve reducing the observation period to 1 hour post-dosing, then subjects will continue to be observed in clinic for 2 to 4 hours during the Day 85 Visit.

#### **Subjects randomized prior to IDMC approval to convert Day 99 Visit to telephone call:**

- If a subject reaches the Day 99 Visit prior to the IDMC approval to convert the Day 99 Visit to a telephone call, the Day 99 Visit must be completed to assess safety parameters, including AEs, vital signs, pulse oximetry, ECG, physical exam, clinical laboratory values, and spirometry. No telephone call is required on this day if a visit is conducted. The Day 99 Visit may occur at any time between Day 88 and Day 99.
- If the IDMC does not approve to convert the Day 99 Visit to a telephone call, subjects will proceed as per the bullet above.

#### **Subjects randomized after IDMC approval to convert Day 99 Visit to telephone call:**

- The Day 99 Visit will be changed to a Day 99 Telephone Call to assess AEs. No visit is required on this day if a telephone call is conducted. The Day 99 Telephone Call may occur at any time between Day 88 and Day 99.

### 8.1.3.3 Planned Pre-visit Subject Contacts

There are 5 planned **pre-visit** contacts to the subject during the study; 4 will occur in Part A and 1 will occur in Part B.

These contacts are to occur:

- Part A: 1 day before the Day 1, Day 29, Day 57, and Day 85 Visits
- Part B: 1 day before the Day 113 Visit

This planned pre-visit contact, which may occur via telephone call, text message, or email, is designed to ensure:

- that subjects remember to withhold their morning dose of study drug in Part A before the Day 29 and Day 85 Visit and in Part B before the Day 113 Visit only if the clinic visit is scheduled within 4 hours after the time of the morning dose,
- that subjects withhold their short-acting bronchodilator for 4 hours before spirometry is performed at the clinic in Part A at the Day 1, Day 29, Day 57, and Day 85 Visits, and in Part B before the Day 113 Visit,
- that subjects withhold long-acting bronchodilators the night before the first and last visit of each treatment period

- that subjects remember to bring their subject diary, all unused study drug, and [REDACTED] back to the clinic in Part A at the Day 29 and Day 85 Visits, and in Part B at the Day 113 Visit, and ETT Visit, if applicable.

All subjects will be asked to return their [REDACTED] at the Part A Day 29 and Day 85 Visits, the Part B Day 113 Visit, [REDACTED] at the Part A Day 85 Visit, the Part B Day 113 Visit, or their ETT Visit, as applicable.

Upon completion of the subject's last study visit and all study procedures, the pre-study medication regimen may be resumed at the discretion of the investigator.

### 8.1.4 Follow-Up

The Safety Follow-up Telephone Call is scheduled to occur 28 days ( $\pm$  7 days) after the last dose of study drug for subjects who complete study drug dosing and for subjects who prematurely discontinue study drug dosing.

Based on a clinical finding during either Treatment Period or during the 28-day Safety Follow-up Period, the investigator may decide to convert the Safety Follow-up Telephone Call into a Safety Follow-up Visit, whereby the subject would be asked to return to the clinic.

### 8.1.5 Early Termination of Treatment

If the subject prematurely discontinues study drug treatment, an ETT Visit should be scheduled as soon as possible after the subject decides to terminate study drug treatment. Subjects who prematurely discontinue treatment will also be required to complete the Safety Follow-up Telephone Call, approximately 28 days ( $\pm$  7 days) after their last dose of study drug.

If the subject withdraws consent for the study, no further evaluations will be performed, and no additional data will be collected. Parion Sciences may retain and continue to use any data collected before such withdrawal of consent.

### **8.1.6            Unscheduled Visits**

Subjects may need to be seen at times other than the scheduled study visits for additional safety assessments, to follow up on changes in clinical status, or to follow up on clinical laboratory or other findings. If an additional study visit occurs, the date and assessments completed during the visit will be documented.

### **8.1.7            Independent Data Monitoring Committee**

An IDMC will be formed for this study. The IDMC will conduct regular, planned reviews of study data with the primary goal of evaluating the safety of the study drug regimen to ensure the subjects' safety (Section 12.3.5). Procedural details of the IDMC's structure and function, frequency of meetings, and data planned for review will be included in the IDMC charter. The IDMC charter will be finalized before the first subject is screened.

## **8.2               Rationale for Study Design and Study Drug Regimens**

### **8.2.1            Study Design**

Part A of this Phase 2a, 2-part, randomized, double-blind, placebo-controlled, incomplete block, multicenter crossover study, in subjects with PCD  $\geq 12$  years of age is designed to evaluate the safety and efficacy of VX-371 formulated with or without HS. In Part B (optional), the safety and efficacy of ivacaftor and VX-371 formulated with or without HS will be evaluated. No controlled clinical study to evaluate the effect of a potential therapeutic agent has been completed at the time this protocol was written in subjects with PCD. Only recently have diagnostic criteria evolved that enable a confirmed diagnosis of PCD. Because many patients have been misdiagnosed in the past, this PCD study will restrict enrollment to only those subjects who meet the rigorous entry criteria.

A randomized, double-blind, placebo-controlled study design was selected for Part A to avoid observer bias and reduce symptoms or outcomes arising from the investigator's or the subject's knowledge of treatment. An incomplete block crossover design wherein subjects are randomized to 1 of 4 treatment sequences (Table 8-1) will enable within-subject comparison of the treatment effects with increased statistical power while maximizing the power for the comparisons anticipated to be of greatest interest. In Part B, administration of ivacaftor will be open-label, but subjects will remain blinded to the inhaled study drug treatment regimen and sequence.

During Part A, a 28-day Washout Period is judged to be of sufficient duration for all subjects to return to their baseline values for FEV1. Multiple comparisons will be made which will provide insight with respect to the effect of VX-371 and inform design options for future studies. Even though 2 different concentrations of saline will be used, the double-blind will be maintained with respect to both 0.17% saline (placebo) and 4.2% HS since each subject will receive treatment with only 1 saline concentration; no subject will cross over from 0.17% saline to 4.2% HS or vice versa. The double blind will also be maintained with regard to VX-371 because allocation to this component will remain unknown to both investigators and subjects.

Given the absence of historical information from prior studies in PCD and the abundance of information in CF, another muco-obstructive disease, several extrapolations have been made

regarding the chosen endpoints from CF studies and applied to this PCD study. Change in ppFEV1 was selected as the primary assessment of efficacy, based on observed effects of hydrating agents in CF, and based on observations that oral antibiotics can increase ppFEV1 in treated PCD patients, which indicates that FEV1 may be an acceptable measure. In addition, 2 quality of life instruments (i.e., questionnaires), the QOL-PCD and SGRQ, will be used. [REDACTED]

While chronic cycling antibiotics are not widely used in PCD patients, the scheduling of study drug with regard to the antibiotic schedule should be controlled while the subject is enrolled in the study as antibiotics may affect spirometry results in the PCD population (Section 8.1.1).

A sample size of approximately 150 subjects randomized is considered feasible and is expected to provide sufficient data to evaluate the safety and efficacy of VX-371 formulated with and without HS in Part A along with the administration of oral ivacaftor in Part B.

Part B was designed to evaluate whether the addition of oral ivacaftor will have an impact on the efficacy of inhaled VX-371. Therefore, no Washout Period between Treatment Period 2 and Treatment Period 3 is necessary.

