**Table 3-1 Study PS-G202: Screening Period**

| Event/Assessment                                 | Screening Period
(Day -38 to Day -5)  |
|--|--|
| Clinic visit                                     | X  |
| Informed consent/assent                          | X  |
| Inclusion/exclusion criteria review a | X  |
| Demographics                                     | X  |
| Medical history                                  | X  |
| Medications review                               | X  |
| Height and weight b                   | X  |
| Pulse oximetry and vital signs c      | X  |
| Full physical examination d           | X  |
| 12-lead ECG e                         | X  |
| Spirometry f                          | X  |
| Single dose of HS to assess tolerability         | X  |
| Serum $\beta$ -HCG g                  | X  |
| Serum FSH h                           | X  |
| Serum chemistry                                  | X  |
| Plasma chemistry i                    | X  |
| Hematology                                       | X  |
| PCD genotype j                        | X  |
| Urinalysis                                       | X  |
| Adverse events and serious adverse events        | Continuous from signing of ICF/assent (if applicable) and initiation of study procedures through the Safety Follow-Up Telephone Call |

- a After obtaining informed consent/assent, inclusion criteria # 4A and # 4B ([Section 9.1](#)), as applicable, must be confirmed prior to initiating any other screening assessments during the Screening Period.
- b Height and weight will be measured with shoes off. BMI will be calculated.
- c Pulse oximetry and vital signs will be performed after the subject has been seated or supine for at least 5 minutes.
- d Physical examination of all body systems, excluding rectal and genitourinary examinations.
- e The ECG will be performed after the subject has been seated or supine for at least 5 minutes. Prior to placing ECG leads, the record will be reviewed for the presence of dextrocardia. Subjects with dextrocardia will have all ECG limb and chest (V) leads reversed.
- f The spirometry assessment will be performed within 60 minutes before the test dose of HS and 60 minutes ( $\pm$  5 minutes) after the test dose of HS. See [Section 8.1.1](#) for more information.

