### 8.1.1 Maintenance of Stable Medication Regimen for PCD

If the subject meets the criteria for study participation and is taking HS at the time of screening, the subject will be instructed to stop their usual regimen of inhaled HS for the duration of the study, beginning at least 28 days before the first dose of study drug in the study and continued through completion of the last study visit. If a subject is not taking HS as part of their ongoing PCD treatment, the Day 1 Visit may be scheduled to occur as soon as 5 days after the Screening Visit, provided that results of all screening procedures have been received. Each subject will be instructed to use an appropriate airway clearance technique throughout the study.

All concomitant medications and airway clearance measures/techniques should be kept on a stable regimen for the duration of the study, other than the discontinuation of use of HS during the Screening Period.

If taking daily chronic or chronic cycling antibiotics, the subject must have been on a consistent regimen for at least 4 months before the Screening Visit. The cycling regimen of antibiotics can be either intermittent monotherapy (e.g., 28 days on/28 days off) or continuous alternating therapy (e.g., 28-day cycles of 2 alternating antibiotics). For patients that take cycling antibiotics, with only 1 antibiotic, the first visit of Treatment Period 1 and Treatment Period 2 should be scheduled to occur on the same day of the subject's antibiotic cycle (e.g., if Day 1 falls on the 4th day of a cycle, Day 57 should fall on the 4th day of the same antibiotic cycle). For patients that take cycling, alternating antibiotics, the first day of Treatment Period 1 and Treatment Period 2 should be scheduled to occur on the same day of the subject's antibiotic cycle with the same drug (e.g., if Day 1 falls on the 4th day of a cycle with antibiotic #1, Day 57 should also fall on the 4th day of the cycle with antibiotic #1). Subjects who are on a stable chronic antibiotic regimen should remain on this regimen through completion of the last study visit.

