### 8.1.2 Screening: Day -38 to Day -5

Screening Visit assessments are listed in [Table 3-1](#).

The Screening Visit will occur between Day -38 and Day -5 before administration of the first dose of inhaled study drug to confirm that the subject meets the inclusion and exclusion criteria for the study. The investigator (or an appropriate authorized designee at the study site) will obtain informed consent and assent (where applicable) from each subject. To prepare for study participation, subjects will be instructed on the study requirements for concomitant medications ([Table 9-1](#) and [Table 9-2](#)).

At the Screening Visit, each subject will receive a test dose of 4.2% HS via a PARI eFlow nebulizer to confirm tolerability of inhaled HS. Pre-dose spirometry will be performed within 60 minutes before the test dose. Post-dose spirometry will be performed 60 ( $\pm$  5) minutes after the test dose. If the subject's post-HS test dose spirometry value shows a 15-percentage point or

greater absolute reduction in ppFEV1 compared to the subject's pre-HS test dose ppFEV1 value, the investigator may either screen fail the subject or administer a short-acting bronchodilator to the subject.

If the subject is treated with a short-acting bronchodilator, spirometry will be repeated at least 10 minutes after administration of the short-acting bronchodilator. If the subject's post-short-acting bronchodilator ppFEV1 value does not return to within 15 percentage points (absolute) of the subject's pre-HS test dose ppFEV1 value, the investigator should screen fail the subject.

If the subject's ppFEV1 returns to within 15 percentage points (absolute) of the pre-HS test dose value, the investigator may provide a short-acting bronchodilator for use before all doses of inhaled study drug are administered.

If the subject experiences a post-HS test dose absolute decline in ppFEV1 less than 15 percentage points, the investigator may choose to provide a short-acting bronchodilator for use before all doses of inhaled study drug are administered.

While subjects can be screened based on evidence supportive of a PCD diagnosis, all subjects must meet the confirmatory diagnostic PCD criteria (including central review, as required) prior to randomization ([Section 9.1](#)).

Screen failures and reason for failure will be documented within the eCRF.

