### 9.1 Inclusion Criteria

Subjects who meet all of the following inclusion criteria will be eligible.

1. Subject (or subject’s legally appointed and authorized representative) will sign and date an informed consent form (ICF) and, where appropriate, assent form.
2. Willing and able to comply with scheduled visits, treatment plan, study restrictions, laboratory tests, contraceptive guidelines, and other study procedures.
3. Willing and able to use the nebulization device as directed by the instructions for use.
4. The subject must have evidence supportive of a PCD diagnosis, based on the following [REDACTED].

[REDACTED]

5. Subjects with ppFEV1 of  $\geq 40$  to  $< 90$  percentage points adjusted for age, sex, and height according to the Global Lung Function Initiative (GLI) predicted values at the Screening Visit, taken 4 hours or more after last dose of short-acting bronchodilators ( $\beta$ -agonists and/or anticholinergics)
6. Non-smoker for the past 90 days prior to the Screening Visit and less than a 5 pack-year lifetime history of smoking, and willing to not smoke while enrolled in the study.
7. Stable regimen of medications and chest physiotherapy for the 28 days prior to Day 1, and no anticipated need for changes during the study period (other than stopping inhaled HS).
8. If currently using daily inhaled HS, must be able to discontinue its use for the duration of the study.
9. If taking daily chronic or chronic cycling antibiotics, has been on a consistent regimen for at least 4 months prior to the Screening Visit. The cycling regimen of antibiotics can be either intermittent monotherapy (e.g., 28 days on/28 days off) or continuous alternating therapy (e.g., 28-day cycles of 2 alternating antibiotics).
10. Clinically stable (as deemed by the investigator) for at least 14 days prior to the Screening Visit with no evidence of significant new or acute respiratory exacerbations, excluding symptoms of allergic (perennial or seasonal) or non-allergic rhinitis.
11. Female subjects of childbearing potential must have a negative serum pregnancy test at the Screening Visit. Females of childbearing potential must have a negative urine pregnancy test at the Day 1, Day 57, and Day 85 Visits before receiving the first dose of study drug in each Treatment Period, respectively. Subjects of childbearing potential and who are sexually active must meet the contraception requirements outlined in [Section 11.6.5.1](#).

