### **10.2.3 Dosing in Clinic**

This study requires that the first dose of study drug during each Treatment Period be taken in the clinic (at the Day 1, Day 57, and Day 85 Visits) while the subject is under observation by the study staff for at least 1 hour after dosing.

The post-dose observation period is generally anticipated to encompass the first hour after dosing at Day 1 and Day 57, at which time spirometry, chest auscultation, pulse oximetry, and vital signs will be repeated. If the subject is doing well and is in no respiratory distress, the subject will be allowed to leave the clinic after this period and will be given 28 days of the study drug for at-home administration. If, however, in the judgment of the investigator, the subject needs to continue to be observed or monitored, the length of the post-dose observation period may be extended.

Until the IDMC allows a 1-hour post-dose observation period at Day 85, subjects who continue into Part B will remain in clinic during the Day 85 Visit for 2 to 4 hours after administration of study drug. The amount of time each subject remains in clinic for observation (2 to 4 hours) may be left up to the discretion of the investigator. Prior to discharge, spirometry, chest auscultation, pulse oximetry, and vital signs will be repeated. If the subject is doing well and is in no respiratory distress, the subject will be allowed to leave the clinic after this period and will be given 28 days of the study drug for at-home administration. If, however, in the judgment of the investigator, the subject needs to continue to be observed or monitored, the length of the post-dose observation period may be extended.

If the subject routinely uses a short-acting bronchodilator prior to any inhalation treatment(s) (i.e., pre-treat), this practice should be continued throughout the study prior to inhalation of the inhaled study drug. If the subject does not routinely pre-treat inhaled medications with a short-

acting bronchodilator, but has demonstrated significant respiratory symptoms after the test-dose of HS at the Screening Visit, as determined by the investigator or an absolute decline in ppFEV1 of  $\geq 15$  percentage points following the first dose of blinded inhaled study drug at Day 1, then the subject should be provided with a short-acting bronchodilator, as needed, and instructed to subsequently pre-treat with this medication prior to all subsequent doses of blinded inhaled study drug.

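### Does the 4.2% hypertonic saline test dose at screening undo the blinding to saline concentration?

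*Protocol*

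**What the plan says.** Protocol 8.2.1 gives one purpose of double-blinding as being to "reduce symptoms or outcomes arising from the investigator's or the subject's knowledge of treatment". It accepts that two saline strengths are used and argues that the blind "will be maintained with respect to both 0.17% saline (placebo) and 4.2% HS since each subject will receive treatment with only 1 saline concentration", adding that "no subject will cross over from 0.17% saline to 4.2% HS or vice versa". That is its whole argument for concentration. For VX-371 itself it relies on concealed allocation, and Protocol 10.10 sets out who may know assignments.

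Elsewhere the protocol gives subjects other contact with HS:

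- **Screening test dose.** Under 8.1.2, "each subject will receive a test dose of 4.2% HS via a PARI eFlow nebulizer to confirm tolerability of inhaled HS". Table 3-1 schedules it as "Single dose of HS to assess tolerability". Under 10.2.1, study drug is also given by PARI eFlow nebulizer.
- **Earlier use.** Regular HS users may enter. Inclusion criterion 8 reads "If currently using daily inhaled HS, must be able to discontinue its use for the duration of the study", and under 8.1.1 "the subject will be instructed to stop their usual regimen of inhaled HS for the duration of the study", starting at least 28 days before the first dose.
- **A possible cue.** Section 10.2.3 provides for a subject who "has demonstrated significant respiratory symptoms after the test-dose of HS at the Screening Visit".

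Part A has three null hypotheses: (1) VX-371 in HS versus placebo, (2) VX-371 versus placebo, and (3) VX-371 in HS versus HS alone. SAP 8.1 names the third as the primary assessment of efficacy.

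**The concern.** The argument in 8.2.1 works by denying subjects a comparison: someone who meets only one concentration has nothing to judge it against. The test dose supplies a reference. Each of the 25 + 25 subjects planned for sequences 3 and 4 will have inhaled 4.2% HS before the first blinded 0.17% dose, and those in sequences 1 and 2 will have met the same strength before. If the solutions feel different, a subject might guess the concentration and hold that belief through both periods.

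Hypothesis 1 is where this would count. No sequence contains both concentrations, so the contrast is wholly between subjects and the crossover does not protect it. The self-reported SGRQ and QOL-PCD would be more open to such a belief than ppFEV1. At stake is whether a positive result for VX-371 in HS over placebo could partly reflect expectation while being reported as fully blinded.

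**Working it through.** **Is there a contradiction?** Section 8.2.1 speaks of treatment with one concentration. The test dose in 8.1.2 is a tolerability check given before randomization. Both statements can be true together; the rationale is incomplete, not wrong.

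**Which comparisons are exposed?** Suppose a belief about concentration adds b to both periods of sequences 1 and 2. The shift is equal in the two periods, so the period effect is unchanged. The VX-371-in-HS and HS means each rise by b, and the other two means do not move.

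- Hypothesis 1: b − 0 = b
- Hypothesis 2: 0 − 0 = 0
- Hypothesis 3: b − b = 0

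A generalized least squares check of the treatment-plus-period model gives 1.00, 0.00 and 0.00 for b = 1, at within-subject correlations of 0, 0.3 and 0.6.

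**Precision of hypothesis 1.** Inputs from Protocol 12.1 and Table 8-1: SD 7 points, two-sided 5% level, 10% dropout, sequences of 50, 50, 25 and 25. With 10% removed, 90 subjects provide VX-371 in HS and 45 provide placebo.

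SE = 7 × √(1/90 + 1/45) = 7 × 0.1826 = 1.278 points. The value is the same at all three correlations.

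**The plan's own figure.** Protocol 12.1 states about 87% power for 4 points. 4/1.278 = 3.130, and Φ(3.130 − 1.960) = Φ(1.170) = 87.9%. The noncentral t with 133 degrees of freedom gives 87.4%. The figure reproduces at 90 versus 45; at 100 versus 50 the normal calculation gives 91.0%.

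**Illustration with an assumed bias.** With no true effect, the rejection rate is 1 − Φ(1.96 − b/SE) + Φ(−1.96 − b/SE). For b = 1, b/SE = 0.7825, so the rate is 1 − Φ(1.1775) + Φ(−2.7425) = 0.1195 + 0.0030 = 12.25%.

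| Assumed bias (ppFEV1 points) | Rejection rate, hypothesis 1 |
|---|---|
| 0 | 5.0% |
| 0.5 | 6.8% |
| 1 | 12.3% |
| 1.5 | 21.7% |
| 2 | 34.7% |

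The t calculation agrees to within about half a percentage point and puts the 10% rate at 0.84 points, which is 0.84/7 = 0.12 SD, or 0.84/4 = 21% of the planned effect. For SGRQ and QOL-PCD the documents give no SD. In SD units the same 0.12 applies at 90 versus 45, and 0.16 if an assumed 60% contribute (54 versus 27). Every bias in this paragraph is assumed.

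**How strong is the cue?**

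- It is one dose, normally 5 to 38 days before Day 1. Earlier HS users have been off HS for at least 28 days.
- Exclusion criterion 10 removes subjects with a history of significant HS intolerance. Under 8.1.2, strong reactors may be screen-failed, and should be if ppFEV1 does not recover after a bronchodilator.
- Bronchodilator pre-treatment under 10.2.3 applies whatever the assigned arm.
- For ppFEV1, Protocol 11.5.1 requires three acceptable maneuvers, 0.15 L repeatability and central quality review. These limit effort effects without excluding them.

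**The case for a change.** The strongest case for a change is that a design rationale should support its own claim. Section 8.2.1 asserts that the concentration blind holds, and its only reason ignores an exposure that the same protocol gives everyone. Section 10.2.3 expects some subjects to notice that exposure. Hypothesis 1 is a formal null with its own power statement, and Protocol 12.1 and 12.3.3.1 list the three nulls unranked. The readable text describes no matching of the solutions and no check of the blind. The remedy would be a few sentences: acknowledge the test dose, call hypothesis 1 supportive and attach a caveat.

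Much of this stands. The rationale is incomplete, the exposure is universal, and hypothesis 1 has no within-subject protection. Two things do not carry over. First, the step from having met HS once to recognizing the concentration during blinded dosing is not in the documents. The Pharmacy Manual and consent pages, where a safeguard might sit, are not available, so a statement that the blind is not assured would go beyond the evidence. Second, the remedy would do little. It changes no procedure or estimate and measures nothing. Ranking hypothesis 1 below the primary comparison largely restates SAP 8.1, to which the protocol defers for statistical detail.

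**Conclusion.** The concern does not call for a change. Section 8.2.1 leaves out a relevant fact, but its sentence is accurate and no stated property of the trial is shown to fail. The omission reaches hypothesis 1 and the matching questionnaire contrasts only; hypotheses 2 and 3, including the primary assessment in SAP 8.1, are unaffected.

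The possible size cannot be fixed from the documents. About 12% false positives for hypothesis 1 depends on an assumed 1-point bias in favor of the HS sequences, SD 7 and 90 versus 45 subjects; with no bias the rate is 5%. The calculation shows how sensitive a between-subject contrast would be, not that a bias exists.

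An analyst reading a positive hypothesis 1 would in any case treat it as a between-subject comparison of products with different saline strengths, beside the primary result. Documentation of matched solutions would strengthen the rationale, and evidence that subjects could identify the concentration would reopen the question. The available documents contain neither.
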